### **9.5.1 Sensitivity Analyses**

One key exploratory analysis will be to explore the time lag over which the effect of the intervention builds up (and/or fades away) by using nonlinear nonparametric modelling of the intervention by time interaction.

Also the analysis in section 9.5 will be repeated for the “on treatment” variable (see section 9.4) according to the actual time of implementation of the intervention in each study site.

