3 STUDY DESIGN

This is a multicentre, stepped wedge cluster randomised trial of a package of care consisting of a management plan for identification and delivery of the 'at risk' fetus, together with strategies for increasing pregnant women's awareness of the need to report decreased fetal movements early. A nested qualitative study will examine the acceptability of the intervention to patients and health care providers and identify process issues (barriers to implementation). Clinical audit (before and after the change in practice) will be used to determine the effect of interventions on process outcomes (eg number of ultrasound scans, number of admissions for induction of labour). The study will take place in participating hospitals in the UK.

The interventions will be introduced over a 33 month period. Data will be collected over a 36 month period.

Data in the 'active phase' after introduction of the intervention will be compared to data in the 'control phase' – the time from study start to the time of introduction of the intervention. Given

that it will take individual units some time (a) to effect change in management in their unit from time of introduction of the intervention and (b) that it will take some time for this change in practice to impact on clinical outcomes, we plan a “washout” period after the introduction of the intervention during which data will not be included in either group for analysis. We anticipate that this washout period will be of two months duration – this will be finalised in the statistical analysis plan.

Outcomes will be measured from routinely collected data. For consistency, we will normally only include data items which become available within four months after the delivery date in question, although we may seek advice from the TSC about exceptions as they arise.

A diagram indicating randomisation of hospital groupings in the stepped wedge design is shown below:

Table 1: Stepped wedge design. Shaded areas indicate periods in which the interventions are being implemented. The order in which hospital groupings implement the interventions will be determined via randomization.

Hospital groupings	Month								
	1-4	5-8	9-12	13-16	17-20	21-24	25-28	29-32	33-36
1-3									
4-6									
7-9									
10-12									
13-15									
16-18									
19-21									
22-24									

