4.3 EXCLUSION CRITERIA

We will exclude women as follows:

- Women for whom data on delivery outcomes is still unavailable four months after the date of delivery

- Women delivering in the “washout” period in each unit.

Members of the trial management group and participants who do not speak/understand English will be excluded from those participating in Q5.

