8 STATISTICS AND DATA ANALYSIS

8.1 SAMPLE SIZE CALCULATION

The sample size is the number of women delivering in hospitals participating in the study. Scotland has around 58,000 deliveries per year with 16 consultant led maternity units, 20 smaller units each delivering less than 350 babies per year, and seven units delivering less than five births per year (Appendix 2). The units involved in Perinatal Ireland (an all-Ireland research consortium across 7 academic centres in Ireland currently funded by the Health

Research Board, Ireland) have 50,000 births per year with seven large centres (Appendix 2). Combining one or two of the smaller units and one larger unit into a single “hospital group” for each local area could provide 24 hospital “groups” – the details of hospital groupings will be reviewed and finalised immediately prior to randomisation.

We calculated statistical power using the methodology for stepped wedge designs proposed in Hussey and Hughes (2007) (26). First, we analysed stillbirth event data from the Scottish Perinatal and Infant Mortality and Morbidity Report (SPIMMR) covering years 2005-2010 (4) to determine estimates of between- and within-unit variability in stillbirth rate. Analysis was by generalized linear mixed model for binary outcomes. The power calculation, as per equations (#7) and (#8) in (26) assumed: significance level 5%; analysis by generalized linear mixed model; deliveries equally distributed across hospital groupings; baseline stillbirth rate 0.438% (4); cluster coefficient of variation 0.333.

Finally, the statistical power depends on the number of groups in which the intervention is implemented at each stage of the stepped wedge design and the duration of recruitment at each “step”. Our study design proposes sequential introduction of the intervention into three hospital groups at a time at four month intervals over a 32 month period. This would give 92.4% power to detect a 30% relative risk reduction under the intervention and 80.7% power to detect a 25% reduction. A 30% risk reduction was seen in the Norwegian study; the anticipated effect sizes of 25% and 30% relative reduction take into account that the intervention will not have the power to reduce all stillbirths, since 20% of stillbirths in Ireland (5) and 15% in Scotland (4) are associated with congenital anomaly.

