## 4 Study Design

### 4.1 Brief Description

AFFIRM is a pragmatic, multi-centre, stepped wedge cluster design trial, in which participating hospitals in the UK will be randomized to the timing of introduction of a care package. The tested intervention is a package of care consisting of a management plan for identification and delivery of the ‘at risk’ fetus, together with strategies for increasing pregnant women’s awareness of the need to report decreased fetal movements early.

Data in the ‘Active Phase’ after introduction of the intervention will be compared to data in the ‘Control Phase’. There will be a washout period of two calendar months after the introduction of the intervention commences during which data will not be included in either group for analysis. Outcomes will be measured from routinely collected data.

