### **7.2 Data analysis**

The statistician at ECTU will perform the statistical programming and analysis to produce all summary tables and figures using the statistical packages SAS (v9.2 or a more recent version), IBM SPSS (version 19 or later) or R, whichever is the most appropriate to use in the National Safe Haven.

In general terms, categorical data will be presented using counts and percentages, whilst continuous variables will be presented using the mean, median, standard deviation (SD), minimum, maximum, inter quartile points at 25% and 75% (Q1 and Q3) and number of patients with an observation (n) in the statistical output,

All statistical tests will be 2-sided and will be performed using a 5% significance level, leading to 95% (2-sided) confidence intervals (CIs) and corresponding p-values, unless otherwise specified.

Distributional assumptions underlying the statistical analyses will be assessed by visual inspection of residual plots. Normality will be examined by normal probability plots. If the distributional assumptions for the parametric approach are not satisfied, further data transformation (for achieving Normality), or other suitable methods will be considered. This will be documented in the statistical results report together with the reasoning supporting the action taken, if applicable.

The Intent-to-treat (ITT) population will be used to summarise all data and all analyses unless otherwise specified.

For the main clinical paper, appropriate MS Word tables will be compiled using the statistical output generated at the National Safe Haven (Examples in Appendix 1)

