## **8 Population for Analysis**

### **8.1 Intent to treat population**

The intention-to-treat (ITT) population will include all babies of women delivering at one of the AFFIRM study maternity units for the duration of the study.

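### SAP 9.5.1 sets out to trace how the effect builds up but does not restore the washout deliveries, so the first two months after introduction are unobserved

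*SAP*

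**What the plan says.** **The analysis.** SAP 9.5.1 names one key exploratory analysis of the primary outcome. Its aim is to "explore the time lag over which the effect of the intervention builds up (and/or fades away"), and it is to be done "by using nonlinear nonparametric modelling of the intervention by time interaction". The section does not give the data set, the time origin or the unit of time. It also plans a repeat of the primary analysis using the date on which each site actually implemented the package.

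**The exclusion.** SAP 4.1 sets a washout of two calendar months after introduction, "during which data will not be included in either group for analysis". Protocol 4.3 lists among the excluded women: "Women delivering in the “washout” period in each unit". Protocol 3 gives the reason: units need time to change their management, and "it will take some time for this change in practice to impact on clinical outcomes". Protocol 3 leaves the length to be finalised in the SAP, and SAP 4.1 finalises it at two months.

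**The population.** SAP 8.1 says that the intention-to-treat population "will include all babies of women delivering at one of the AFFIRM study maternity units for the duration of the study", and it does not mention washout. SAP 7.2 makes this population the default for all analyses, and SAP 9.5 uses it for the primary outcome.

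**The concern.** By the protocol's own account, the washout is the period in which practice is changing and the effect is starting to appear. An analysis of how the effect builds up is therefore most interested in the two months that the general exclusion rule removes.

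Two questions depend on those months. One is how soon a unit adopting the package sees any change. The other is whether a two-month washout was needed at all or discarded usable data. No other planned analysis addresses either one: the on-treatment repeat moves the implementation date but does not vary the washout.

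**Working it through.** **Inputs.**
- 24 hospital groups, three per step, eight steps four months apart (protocol 8.1); 36 months of data (protocol 3).
- 58,000 deliveries a year in Scotland and 50,000 births a year in the Perinatal Ireland units (protocol 8.1). Together 108,000 a year, or 324,000 over three years.
- "baseline stillbirth rate 0.438% (4); cluster coefficient of variation 0.333" (protocol 8.1).
- "All statistical tests will be 2-sided and will be performed using a 5% significance level" (SAP 7.2).
- Assumed: equal groups and steps taken on time.

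**1. The plan's own power figures.** In the Hussey and Hughes model, I = 24 groups, T = 9 periods and 324,000 / 216 = 1,500 deliveries per group-period.
- σ² = 0.00438 × 0.99562 / 1,500 = 2.907 × 10⁻⁶.
- τ² = (0.333 × 0.00438)² = 2.127 × 10⁻⁶.
- Design sums: U = 108, W = 1,836, V = 612.
- Var = Iσ²(σ² + Tτ²) / [(IU − W)σ² + (U² + ITU − TW − IV)τ²]. The bracketed coefficients are 756 and 3,780, so Var = 1.503 × 10⁻⁷ and SE = 0.000388.
- 30% reduction: 0.001314 / 0.000388 − 1.96 = 1.43, power 92.4% (protocol: 92.4%).
- 25% reduction: 0.001095 / 0.000388 − 1.96 = 0.86, power 80.6% (protocol: 80.7%).
- Dropping half the deliveries from each group's first active period, by weighted least squares: 88.5% and 75.0% (protocol: 88.2% and 74.6%).

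The inputs therefore match the plan's design. These powers belong to the primary analysis, which this point leaves alone.

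**2. What washout removes.**
- Post-introduction time: sum over k = 1 to 8 of 3 × (36 − 4k) = 432 group-months.
- Washout: 24 × 2 = 48 group-months; 48 / 432 = 11.1%. Remaining: 384 (88.9%).
- Deliveries: 324,000 / 864 = 375 per group-month; 48 × 375 = 18,000.
- Stillbirths at the baseline rate: 18,000 × 0.00438 = 78.8.

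| Months since introduction | Groups contributing | Group-months | Under the washout rule |
|---|---|---|---|
| 0–2 | 24 | 48 | excluded |
| 2–4 | 24 | 48 | kept |
| 4–8 | 21 | 84 | kept |
| 8–12 | 18 | 72 | kept |
| 12–16 | 15 | 60 | kept |
| 16–32 | 12, falling to 3 | 120 | kept |

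**3. What can and cannot be learned.** Compare an effect present in full from day 1 with one that grows to its full size by month 2. Both are zero before introduction and full from month 2 onward. They differ only in months 0–2, where no data are kept, so the retained data fit both equally well. For the same reason, the retained data cannot show that the washout was longer than needed.

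Slower build-up remains partly visible. The documents give no shape, so these are assumptions. For linear build-up over L months, the share still to come after month 2 is 1 − 2/L:
- L = 2: 0%
- L = 3: 33%
- L = 4: 50%
- L = 6: 67%
- L = 12: 83%

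For exponential build-up with half-life h months, the share is 0.5^(2/h): 25% for h = 1, 50% for h = 2 and 71% for h = 4.

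**4. What restoring the deliveries would give.** The same mixed model was fitted by weighted least squares with separate effects for 0–2, 2–4, 4–8, 8–12 and 12 or more months, and within-cluster variance at the average of the baseline rate and a 30% lower rate.
- Months 0–2: SE 12.0% of the baseline rate; 1.96 × 12.0 = 23.5, so a 95% interval of about ±24% of the baseline rate.
- Months 2–4: SE 12.0% with or without the washout deliveries.
- Months 2–4 against 12 or more months, washout excluded: SE 13.5%. A difference of (1.96 + 0.84) × 13.5 = 38% of the baseline rate would be needed for 80% power.

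**The case against.** A reader might infer that the analysis cannot see the build-up at all. The documents do not support that. Of post-introduction time, 88.9% remains, every group contributes months 2–4, and the first three groups run to month 32. Build-up is wholly hidden only if it is complete within two months. Fade-away, which the same sentence of the SAP covers, is hardly touched. Nor is it right that the trial could not tell whether the washout was too short: an effect still growing after month 2 would be the sign, subject to the limited precision above. That is also the case that would bias the primary estimate. A washout that was too long costs power only.

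Two other inferences fail. The length is no longer provisional, because SAP 4.1 fixes it. The fall in power from 92.4% to 88.2% is not a cost of this omission, because the remedy keeps the primary exclusion and recovers none of it.

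A fair defence is that the SAP never says the exclusion applies to 9.5.1: section 4.1 concerns membership of the two compared groups, and 8.1 carries no exclusion. This does not settle the matter. The primary analysis uses the same intention-to-treat population, so reading 8.1 as admitting washout deliveries would admit them there too, against 4.1. The coherent reading is that the exclusion applies throughout unless lifted. On either reading, 9.5.1 should name its data set.

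The objection on precision stands. With about 79 stillbirths, the restored window will not tell a unit with any confidence how soon to expect fewer stillbirths.

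**Conclusion.** The point holds in a limited form. Under the exclusion in SAP 4.1 and protocol 4.3, with no exception in 9.5.1, months 0–2 of the time-lag curve are unobserved: 11.1% of post-introduction group-months, about 18,000 deliveries and about 79 stillbirths. The analysis then cannot distinguish an immediate effect from one complete by month 2, and cannot show that a shorter washout would have sufficed. It can still address later build-up, fade-away and a washout that was too short.

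The counts assume equal groups, on-time steps and the protocol's annual delivery figures. The standard errors also assume the protocol's coefficient of variation and the variance stated in step 4. Using the baseline-rate variance instead would raise the months 0–2 figure to at most 12.0 × √(0.00438 / 0.003723) = 13.0% of the baseline rate. The primary estimate and its power are unaffected, so this is an inexpensive improvement to an exploratory analysis that the SAP itself calls key.

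**What to change.** - Keep the washout exclusion in the primary analysis.
- In SAP 9.5.1, state that the time-lag model alone includes washout deliveries. Code exposure as time since introduction from month 0, and zero before introduction. Say whether introduction means the randomised or the actual date, and use a finer unit than the four-month study periods in SAP 3.2.
- Show the fitted curve with its confidence band and a mark at two months.
- Word the washout exclusion in SAP 4.1 and protocol 4.3 as applying to the active versus control comparison.
- Optionally, fit the same model to induction of labour. It is already a secondary outcome and, if events are more frequent than stillbirths, would show onset more clearly.

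**Cost.** A sentence or two in the SAP, one modified exploratory model, and a wording change to protocol 4.3, which under protocol 13.1 goes to the ethics committee and local R&D. The team must also confirm that the extracts hold the washout deliveries. The documents do not say so, and protocol 6.2 allows for study-specific collection outside Scotland and Ireland. The report should state that the months 0–2 stillbirth estimate is imprecise.

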### **9.5.2 Subgroup analyses**

A priori subgroups for the primary analysis will be explored for babies with and without fetal abnormalities. This analysis will be performed by including an interaction term between intervention and the relevant covariate in the model described in Section 9.5 above. A stricter level of statistical significance ( $p < 0.01$ ) will be used in this analysis to reflect its exploratory nature.

## **9.6 Discrete Secondary Outcomes**

For the following binary outcome measures, we will use the same methods as for the primary outcome analysis which included adjustment for patient level covariates:

### **9.6.1 Stillbirth at 28 weeks gestation and above (WHO definition)**

### **9.6.2 Stillbirth at 22 weeks gestation and above**

### **9.6.3 Stillbirth at 37 weeks gestation and above**

### **9.6.4 Stillbirth amongst normally formed infants of 22 weeks gestation and above, 24 weeks gestation and above, 28 weeks gestation and above and 37 weeks gestation and above**

### **9.6.5 Perinatal mortality**

### **9.6.6 Rates of caesarean section**

### **9.6.7 Rates of induction of labour (overall)**

### **9.6.8 Rates of elective delivery (induction of labour and caesarean section prior to the onset of labour) overall**

### **9.6.9 Rates of induction of labour at 39 weeks 0 days gestation or later**

### **9.6.10 Rates of elective delivery (induction of labour and caesarean section prior to the onset of labour) in women delivered at 39 weeks 0 days gestation or later**

### **9.6.11 Rates of admission to the neonatal unit**

### **9.6.12 Rates of admission to the neonatal unit for more than 48 hours**

**9.6.13 Rates of admission to the neonatal unit for term babies (those born at 37 weeks 0 days or greater)**

**9.6.14 Proportion of babies with fetal growth restriction**

**9.6.15 Rates of spontaneous vaginal delivery**

**9.6.16 Proportion of babies born preterm**

## **9.7 Continuous Secondary outcomes**

For the following continuous outcomes a mixed linear regression model will be used to compare the means between the intervention groups adjusting by a random effect for site and fixed effects for the intervention implementation and study time periods. The result will be presented as an adjusted difference in means together with its corresponding 95% CI and p-values:

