Adjustment will be made for the following variables: (maternal age, maternity unit of delivery, parity, smoking status, maternal BMI, number of babies [one or more] and ethnicity)

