8.2 PROPOSED ANALYSES

For the binary outcomes being addressed in research questions Q1-Q4, data will be analysed by generalized linear mixed model with a random effect for hospital group and fixed effects for the intervention implementation and study time period. Data will be analysed on an intention to treat basis (the design of the trial means it is not possible to determine individual patient /caregiver compliance with the intervention). There will be no imputations for missing data. Subgroup analyses will include those with and without congenital anomalies. No interim analyses will be performed other than those requested by the trial steering committee, who will be the only group to view the interim analyses. A full statistical analysis plan will be developed and signed off prior to locking of the study database.

For research question Q5, the qualitative data will be audio recorded and transcribed. The data will be coded thematically and an analytical framework developed to make sense of patient experience of fetal movement and the intervention and also health care providers’ perspectives and experiences. NVivo will be utilised to support the analysis. The RA and [name] will work together to ensure rigour and validity.

The process outcomes being assessed in Q6 (rates of induction of labour, number of women presenting with decreased fetal movements, interval between perceiving fetal movements and presenting to hospital) will be analysed using the same methods as for Q1-Q4, with the exception of the continuous outcome (interval between perceiving fetal movements and presenting to hospital) which will be analysed in a normal linear mixed model.

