### 9.5 Primary Outcome

The primary outcome will be summarised overall, and by study site and active/control periods expressed as a rate per 1000 live births. Number of stillbirths (CEMACH definition) will be analysed on an intention to treat basis, incorporating all patients in the ITT population for whom outcome data are available. The number of stillbirths will be compared before and after implementation of the Active intervention using a logistic regression generalised linear mixed model following the model structure described in Hussey and Hughes [3]. The effect of implementation of the Active intervention will be presented as an odds ratio and its 95% CI. The intervention groups will be ordered in such a way that an odds ratio of less than one corresponds to a benefit for Active Phase over Control Phase

The event rate  $\mu_{ij}$  in site  $i$ , study period  $j$  will be modelled in the linear component of the logistic regression as:

$$\mu + \alpha_i + \beta_j + \theta X_{ij}$$

where:  $\mu$  is the overall mean event rate on the logit scale;

$\alpha_i$  is a zero-mean random effect for site  $i$ ,  $\alpha_i \sim N(0, \tau^2)$ ;

$\beta_j$  is the fixed effect log-odds ratio for time period  $j$ , with  $\beta_1=0$  for identifiability;

$\theta$  is the fixed effect log-odds ratio for the intervention;

$X_{ij}$  is a (0/1) variable to indicate whether the intervention is implemented in site  $i$  during period  $j$ .

A site by intervention interaction random effect will be included in the model and retained if it is found to explain an important proportion of the variability in outcomes.

The patient-level covariate included will be maternal age and number of babies (one; more than one).

A secondary analysis adjusting for a full list of patient-level covariates will also be included (maternal age, parity, smoking status during pregnancy, maternal BMI, number of babies (one or more) and ethnicity). This will be performed as a complete-case analysis.

A further secondary analysis not adjusting for patient level covariates will also be performed.

Also, a Scotland only model will be generated with the patient-level covariates included in the primary analysis plus the deciles of deprivation.

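### SAP 9.7 models the continuous secondary outcomes without the patient-level covariates used for the binary outcomes in 9.6, at a small, avoidable cost in consistency and precision

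*SAP*

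**What the plan says.** SAP 9.7 compares means for three outcomes (gestation at delivery in women having induction, gestation at delivery, and birthweight centile) "adjusting by a random effect for site and fixed effects for the intervention implementation and study time periods". It names no patient-level covariate and does not refer back to 9.5. It then says: "The result will be presented as an adjusted difference in means together with its corresponding 95% CI and p-values".

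SAP 9.5 puts two patient-level covariates in the primary model: maternal age and number of babies (one, or more than one). It adds, for the primary outcome, a complete-case analysis on a longer covariate list and an analysis with no patient-level covariates. SAP 9.6 carries the adjustment into its binary outcomes: "we will use the same methods as for the primary outcome analysis which included adjustment for patient level covariates".

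Protocol 2.2.2, after listing the secondary endpoints and the data to be collected, says "Adjustment will be made for the following variables". It names maternal age, maternity unit, parity, smoking, BMI, number of babies and ethnicity, and does not restrict the statement to any type of outcome. Protocol 8.2 describes the analysis of the binary outcomes as a "generalized linear mixed model with a random effect for hospital group and fixed effects for the intervention implementation and study time period". It names no patient-level covariate there, and none for its one continuous process outcome.

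**The concern.** Two pairs of outcomes measure nearly the same thing under different models. Preterm birth (9.6.16) is a cut of gestation at delivery (9.7.2); the first is adjusted and the second is not. Growth restriction undelivered at or after 40 weeks (9.6.14) uses a 10th-centile cut of size at birth, and birthweight centile (9.7.3) is the continuous measure; again only the first is adjusted. If the two members of a pair disagree, the reader cannot tell whether the covariate set is the cause.

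The wording also leaves room for choice at the analysis stage. The 9.7 result is labelled adjusted, and the protocol promises patient-level adjustment, but the stated model adjusts only for site and period.

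Finally, number of babies plausibly predicts gestation strongly and is already in the primary model. Leaving it out puts explainable variation into the residual.

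**Working it through.** **The plan's own figure.** The documents give no SD, ICC, power or precision for the continuous outcomes. The only figure against which the stepped-wedge variance can be checked is the power in Protocol 8.1.

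- Inputs from Protocol 8.1: 24 hospital groups, three crossing over every four months (Protocol section 3, Table 1, shows nine periods); baseline rate 0.00438; cluster coefficient of variation 0.333; two-sided 5%; 58,000 + 50,000 = 108,000 births a year.
- Cell size: 108,000 × 3 years = 324,000; 324,000 / (24 × 9) = 1,500.
- Model: random site intercept with SD 0.333 × 0.00438, fixed period effects, individual variance 0.00438 × (1 − 0.00438). Power = Φ(δ/SE − 1.96), with δ equal to 30% or 25% of the baseline rate.
- Without washout: 92.4% and 80.6%; the protocol states 92.4% and 80.7%.
- With half of each group's first active period removed (24 × 750 = 18,000 births, leaving 306,000): 88.5% and 75.0%; the protocol states 88.2% and 74.6%.

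The variance formula therefore reproduces the plan closely enough to use for a continuous outcome.

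**Baseline precision for a continuous outcome.** With 306,000 births, total SD set to 1 and an assumed ICC of 0.001 to 0.05, the 95% half-width without covariates is about 0.013 SD. At an assumed gestation SD of 1.9 to 2.1 weeks this is 0.013 × 1.9 = 0.025 to 0.013 × 2.1 = 0.027 week.

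**What number of babies explains (gestation, all births).** Assumptions, none from the documents: share of babies from multiple pregnancies f = 0.03; gap in mean gestation d = 3 to 4 weeks; overall SD = 1.9 to 2.1 weeks. For a two-group covariate, R² = f(1 − f)d²/SD², with f(1 − f) = 0.0291. The interval ratio is √(1 − R²).

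| d (weeks) | SD (weeks) | R² | Interval ratio |
|---|---|---|---|
| 3 | 2.1 | 0.0291 × 9 / 4.41 = 0.059 | 0.97 |
| 4 | 1.9 | 0.0291 × 16 / 3.61 = 0.129 | 0.93 |

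The interval is about 3% to 7% narrower. Multiplying the residual variance in the stepped-wedge model by (1 − R²) agrees with the simple formula: the SE ratio is about 0.975 at R² = 5% and 0.95 at R² = 10%, nearly independent of the ICC.

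**In absolute terms.** The half-width falls by 0.03 × 0.027 = 0.0008 week at the low end and 0.067 × 0.025 = 0.0017 week at the high end.

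**The other two outcomes.** The calculation does not carry over. Among induced women the share of multiples and the gestation gap may differ, and for birthweight centile the relevant gap is on another scale. The documents give nothing from which to set either.

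**The case against.** The best defence is that this changes nothing of substance. A half-width of about 0.026 week is already far finer than any shift in gestation likely to matter, and a saving of 0.001 to 0.002 week will not alter a conclusion. That stands, and it is why the point is minor.

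It can also be said that 9.7 follows the structure of Protocol 8.2, which names no patient-level covariates. That stands in part: the protocol is not consistent within itself. A reader might infer that 9.7 alone breaks the protocol's list, but the documents do not support this. The models in 9.5 and 9.6 use only two of the six patient-level variables on the list, and the longer list appears only in a secondary analysis of the primary outcome. What is particular to 9.7 is that patient-level adjustment disappears altogether, without explanation.

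Three other readings go too far:

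- That every binary outcome is adjusted. The Apgar thresholds and resuscitation at birth (SAP 9.8) are only summarised, so the contrast is with the outcomes modelled in 9.6.
- That a changing multiple-birth rate would bias the estimate. The 9.7 model has fixed period effects, which absorb any trend common to the sites. A 0.3-point difference in the share of multiples between phases corresponds to 0.003 × 3 = 0.009 to 0.003 × 4 = 0.012 week, but that compares crude phase totals, which the model does not do. Only site-specific or chance imbalance in case mix remains.
- That precision is known to be lost for birthweight centile or for induced women. No figure supports this.

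**Conclusion.** The inconsistency is clear from the text: 9.7 omits the covariates that 9.6 carries over, Protocol 2.2.2 does not confine adjustment to binary outcomes, and no reason is given. The stronger grounds for changing it are that linked outcomes should share a covariate set and that the model should be fixed in advance. Precision is a lesser ground: about 3% to 7% of interval width for gestation in all births, resting wholly on the assumed 3% multiples, 3 to 4 week gap and SD of 1.9 to 2.1 weeks, and very small in absolute terms at around 300,000 women. This is a free improvement of minor importance, not a threat to the trial's conclusions.

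**What to change.** In SAP 9.7, add maternal age and number of babies as patient-level fixed effects, as in 9.5 and 9.6, and report the model without them as the secondary version, as 9.5 does for the primary outcome. This aligns 9.7 with the primary model. It does not bring either section up to the full list in Protocol 2.2.2, and the SAP should not imply that it does.

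The cost is one line of text. Both variables are already needed for the primary model. Version 3.0 of the SAP was revised for missing covariate data and uses these two in the primary analysis, so missing values are unlikely to be an obstacle; that is an inference, since the documents give no missingness rates.
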